A clinical evaluation will be carried out (doctor/nurse) at the commencement of cetuximab, every week during radiotherapy and for four weeks following completion of treatment to record blood count, biochemical profile, estimated GFR, and toxicity scores (using NCI CTC V.3.0). Serum magnesium is to be monitored weekly for 8 weeks post completion of cetuximab treatment. In patients on anticoagulants or those with an abnormal initial clotting profile, clotting profile is measured weekly during chemotherapy then weekly for four weeks post-termination (and longer if deemed clinically appropriate) if this is abnormal.

An MRI scan will be carried out at six weeks following radiotherapy completion then an attempt at surgery will take place eight weeks post radiotherapy completion.

Following surgery, adjuvant chemotherapy is given according to the discretion of the treating physician but recorded on the relevant CRF.

A sample of formalin-fixed paraffin-embedded tumour tissue removed during surgery will be sent to a central lab for analysis of KRAS mutation status. The tumour tissue will be stored and used in future research studies if the patient has consented to this. Otherwise, it will be returned to the site.

From the point of view of late toxicity, patients will be assessed at 6, 12, 24 and 36 months post completion of radiotherapy.

On confirmed tumour progression further formal follow-up within the trial ceases apart from ultimately recording date and cause of death. Further clinical management, including second-line chemotherapy is at the discretion of the treating physician. On study withdrawal for any reason then the CRF Off Study Form is completed, providing reason for treatment withdrawl and/or complete withdrawl. On patient death, CRF Death Form is (also) completed.

No other concomitant cytotoxic treatment or radiotherapy is permitted during the trial.

Specified dose limiting toxicities:

All toxicities below must adhere strictly to definitions specified in the National Cancer Institute Common Terminology Criteria for Adverse Events v3.0:

 Grade 3 diarrhoea that does not improve to grade 2 or less, within 24 hours on intensive anti-diarrhoeal therapy

- o Grade 4 diarrhoea
- Grade 3 or 4 fatigue
- Grade 3 or 4 neutropenia accompanied by fever (>38°C) or ≥grade 3 infection
- Grade 4 thrombocytopenia (platelet count < 25×10^{9} /L)
- o Grade 4 nausea/vomiting despite full antiemetic treatment

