8.2 Treatment details

8.2.1 Treatment summary

Patients will be treated with pelvic radiotherapy to a planned volume at a dose of 45 Gy in 25 daily fractions of 1.8 Gy treating 5 days per week from Monday-Friday.

Concurrently they will receive oral capecitabine at 650 mg/m² bd 5 days per week from Monday-Friday on the days of radiotherapy only.

In addition, they will receive a loading dose of iv cetuximab at 400 mg/m² one week before the commencement of radiotherapy then at 250 mg/m² once per week during weeks 1, 2, 3, 4 and 5 radiotherapy i.e. six doses of cetuximab in total.

In addition they will receive iv irinotecan at 60 mg/m² once per week for four doses in total during weeks 1, 2, 3 and 4 of radiotherapy. Administration of irinotecan follows the administration of cetuximab.

Antiemesis: Prior to weekly treatments including iv irinotecan and cetuximab it is recommended that patients will receive premedication using a 5HT3 antagonist such as 8 mg iv ondansetron plus a steroid such as 8 mg iv dexamethasone (in addition they will receive an antihistamine such as 10 mg iv chlorpheniramine to reduce the likelihood of a cetuximab-related infusion reaction). Prior to treatment with iv cetuximab alone, it is recommended that patients receive an antihistamine plus steroid. Oral antiemetics following iv infusions including irinotecan might include dexamethasone for one or two days but otherwise antiemetics such as metaclopramide or domperidone are to be used as required according to standard local practice.

Patients may have a Hickman line or peripherally inserted central catheter (PICC) inserted at the physician's discretion if required to give adequate venous access for the administration of cetuximab and irinotecan. In these patients prophylactic warfarin should not be given because of the interaction between warfarin and capecitabine. Body surface area (BSA) will be calculated using actual body weight and no dose capping is carried out. No change in the dose calculation is carried out for obese patients.

No dose banding is carried out for irinotecan or cetuximab although it is for capecitabine (detailed in Section 8.2.2).

Instructions for storage use and handling of each drug should be according to each SmPC and hospital policies.

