Capecitabine side effects: The side effect profile of capecitabine is similar to 5FU. The main toxicities are hand-foot syndrome, diarrhoea, nausea and stomatitis. Vomiting, fatigue, abdominal pain, dermatitis, fever, parasthesia, headache, dizziness, insomnia, anorexia and a drop in white blood cells are also experienced.

Occasionally, the following problems have been reported: taste disturbance, chest pain, angina pectoris, abnormal drowsiness or lethargy, weakness, dehydration and alopecia.

Capecitabine is contraindicated in patients with moderate or severe renal impairment. Antacids containing aluminium hydroxide may interfere with the absorption of capecitabine and so an alternative should be prescribed if possible.

Capecitabine precautions: Altered coagulation and/or bleeding have been reported in patients taking coumarin-derivative anticoagulants concomitantly with capecitabine. These events occurred within several days and up to several months after initiating capecitabine and also within one month of stopping capecitabine. Patients should be monitored regularly (twice weekly during CRT) for alterations in their coagulation parameters.

Phenytoin plasma concentrations have been shown to increase when used concomitantly with capecitabine. Again, patients should be regularly monitored for increase in phenytoin plasma concentrations and associated clinical symptoms.

Capecitabine should not be administered together with sorivudine [an antiviral] or its chemically related analogues such as brivudine. A chemically significant drug-drug interaction between sorivudine and 5FU, resulting from the inhibition of dihydropyrimidine dehydrogenase [DPD] by sorivudine has been described in literature. This interaction is potentially fatal as it leads to increased fluoropyrimidine toxicity.

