9.1 Assessment investigations

9.1.1 Baseline: Prior to registration

- MRI scan (within 35 days of registration)
- FBC, U&Es, LFTs, serum magnesium (within 7 days)
- Calculated GFR (within 7 days) using Cockcroft formula (Appendix 4) (if ≤ 50ml/min, formal measurement using 24 hour urine/EDTA)
- CEA (within 4 weeks)
- Clotting profile (within 4 weeks)
- Vital signs: blood pressure, pulse rate, temperature (within 7 days)
- Height & weight (within 7 days)
- WHO performance status (within 7 days)
- Baseline toxicity assessment (using NCI CTCAE V.3.0)

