9.1.2 During treatment phase: within 48 hours prior to cetuximab/irinotecan

infusions

Weekly

- FBC, U&Es, LFTs
- Calculated GFR using Cockcroft formula (Appendix 4) (if ≤ 50ml/min, formal measurement using 24 hour urine/EDTA)
- Clotting profile if abnormal at baseline
- Serum Magnesium
- Toxicity assessment (using NCI CTCAE v3.0)
- Capecitabine compliance
- Blood samples for ancillary studies (at start of CRT only) if patient has consented to these (see Section 19)

During each cetuximab infusion

• Vital signs (blood pressure, temperature, pulse, respirations) to be monitored before during and immediately on completion of infusion, and 1 hour post-infusion.

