9.1.3 Post chemoradiation

Weekly for 4 weeks

- FBC, U&Es, LFTs
- Serum Magnesium (continue for 8 weeks in total or until magnesium has normalised; whichever is the longer)
- Toxicity assessment (using NCI CTCAE v3.0)

6 weeks post chemoradiation

- CEA
- Pelvic MRI scan

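### Clotting tests for anticoagulated patients: Section 8.2.2 asks for twice weekly, Section 8.1 for weekly, and the Section 9 lists omit the anticoagulant trigger and the post-treatment tests

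*Protocol*

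**What the plan says.** Four parts of the protocol deal with clotting tests during and after treatment.

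- **Section 8.2.2**, in its precaution on coumarin-derivative anticoagulants, describes altered coagulation and bleeding and gives the timing: "These events occurred within several days and up to several months after initiating capecitabine and also within one month of stopping capecitabine". It then directs: "Patients should be monitored regularly (twice weekly during CRT) for alterations in their coagulation parameters".
- **Section 8.1** sets a rule for a wider group: "In patients on anticoagulants or those with an abnormal initial clotting profile, clotting profile is measured weekly during chemotherapy". It continues: "then weekly for four weeks post-termination (and longer if deemed clinically appropriate) if this is abnormal".
- **Section 9.1.2**, the weekly on-treatment list, has one line: "Clotting profile if abnormal at baseline". The baseline value it refers to is set in Section 9.1.1: "Clotting profile (within 4 weeks").
- **Section 9.1.3**, the list for after chemoradiation, contains no clotting test. It does contain a conditional item of the same kind for another measure: "Serum Magnesium (continue for 8 weeks in total or until magnesium has normalised; whichever is the longer").

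Figure 11 in Section 9.4 marks clotting only before registration. Anticoagulated patients can enter the trial. Section 5.2 excludes those judged unfit for surgery because of coagulation problems, and Section 8.2.1 bars only prophylactic warfarin in patients with a central line: "In these patients prophylactic warfarin should not be given because of the interaction between warfarin and capecitabine".

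**The concern.** Three things do not fit together.

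1. **Frequency.** Coumarin users belong to the Section 8.1 group of patients on anticoagulants. Two frequencies therefore apply to the same people over the same weeks, and neither section refers to the other.
2. **Trigger.** Section 8.1 has two alternative triggers: being on an anticoagulant, or an abnormal initial profile. Section 9.1.2 keeps only the second. The hazard described in 8.2.2 arises after capecitabine is started, so one pre-treatment reading that may be four weeks old is a poor substitute for the first trigger.
3. **After treatment.** Section 8.1 continues weekly testing for four weeks when the profile is abnormal, and Section 9.1.3 does not list it. The month after stopping capecitabine is a period that 8.2.2 itself names as one of risk.

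What is at stake is patient safety. A site that runs its visits from Section 9 could miss on-treatment tests in an anticoagulated patient with a normal baseline, and post-treatment tests in a patient whose profile is abnormal.

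**Working it through.** The protocol gives no count of clotting tests to reproduce. The check compares the rules side by side and multiplies frequency by duration.

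**Inputs**

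- Length of capecitabine and radiotherapy: 5 weeks (Section 8.2.2).
- Cetuximab loading dose one week earlier, so 6 weekly infusions in all (Section 8.2.1).
- Frequency for coumarin users: 2 per week during CRT (Section 8.2.2).
- Frequency for anyone on an anticoagulant or with an abnormal initial profile: 1 per week (Section 8.1).
- Frequency if baseline was abnormal: 1 per week; otherwise none (Section 9.1.2).
- After treatment, if abnormal: 1 per week for 4 weeks, longer if clinically appropriate (Section 8.1); nothing listed (Section 9.1.3).

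**Tests over the 5 weeks of CRT = frequency × 5**

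| Patient | 8.2.2 | 8.1 | 9.1.2 |
|---|---|---|---|
| On a coumarin, baseline abnormal | 2 × 5 = 10 | 1 × 5 = 5 | 1 × 5 = 5 |
| On a coumarin, baseline normal | 2 × 5 = 10 | 1 × 5 = 5 | 0 |
| On another anticoagulant, baseline normal | no rule | 1 × 5 = 5 | 0 |
| No anticoagulant, baseline abnormal | no rule | 1 × 5 = 5 | 1 × 5 = 5 |

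Section 9.1.2 also covers the loading-dose week, so its 5 becomes 6 if that week is counted.

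**Tests in the 4 weeks after treatment, profile abnormal**

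- Section 8.1: 1 × 4 = 4 at least.
- Section 9.1.3: 0.

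**Reading the table**

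- The sections agree only in the last row, where the patient takes no anticoagulant.
- For coumarin users, following 8.1 alone gives 5 / 10 = half of what 8.2.2 asks.
- An anticoagulated patient with a normal baseline, or one who starts an anticoagulant after the baseline sample, is not listed for any test in 9.1.2.
- The gap in 9.1.3 cannot be put down to Section 9 leaving out conditional tests. Section 9.1.3 has the magnesium extension, and 9.1.2 has conditional lines for clotting and for a formal GFR.
- Section 8.1 itself refers sites to Section 9 for the detail of baseline and pre-treatment blood tests, clotting among them. It is therefore realistic that a site would work from the Section 9 lists.

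**The case against.** The strongest reply is that the sections can be read together. Section 8.2.2 is the specific rule for coumarins and 8.1 the general one, and testing twice weekly satisfies both. Section 8.1 states the anticoagulant trigger and the post-treatment tests expressly, and nothing ranks the Section 9 lists above it. On that view Section 9 is incomplete rather than contradictory, and no test is lost unless a site overlooks 8.1 and 8.2.2.

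The exposed group is also small. Patients unfit for surgery because of coagulation problems are excluded, and prophylactic warfarin is barred in those with central lines. A patient established on a coumarin will often have an abnormal baseline and so be caught by 9.1.2, although that is an inference the protocol does not state. Figure 11 is a summary chart, so its silence is not a rival schedule.

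Much of this stands as a limit on size. The count of zero tests applies to a subset only, and the 10, 5 and 0 should not be taken as the expected effect across anticoagulated patients. It does not reconcile the text, however. Section 8.1 makes no exception for coumarins, no section defers to another, and 9.1.2 restates the 8.1 rule with one of its two triggers missing. A site that follows the Section 9 lists in good faith would test less than the protocol requires elsewhere.

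**Conclusion.** The point holds. The clotting instructions conflict on frequency for coumarin users, and Section 9 drops one on-treatment trigger and the conditional post-treatment tests.

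Per coumarin user, the difference is 10 against 5 tests during CRT, falling to 0 under 9.1.2 if baseline was normal. After treatment it is at least 4 against 0 when the profile is abnormal.

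These counts assume the full five-week course and four weeks of follow-up testing. The number of anticoagulated patients is not given, so no total can be estimated. The inconsistency should be corrected because it concerns a bleeding interaction that the protocol describes. The R0 resection rate, the sample size and the analysis are unaffected.

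**What to change.** - **Section 9.1.2:** replace the clotting line with a weekly test for any patient who is on an anticoagulant or had an abnormal baseline, rising to twice weekly during CRT for those on a coumarin.
- **Section 8.1:** state the same rule, with a reference to 8.2.2.
- **Section 9.1.3:** add a weekly clotting test for four weeks, or longer where clinically appropriate, if the profile is abnormal.
- **Figure 11:** add a footnote to the clotting row giving these conditions.

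The cost is wording in three sections and one footnote. Compared with 8.1 alone, a coumarin user has up to 10 − 5 = 5 more blood tests, all of which 8.2.2 already asks for. The post-treatment tests can be taken with the weekly bloods that 9.1.3 already schedules for those four weeks.

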8.2.3 Cetuximab

Administration: Cetuximab is given intravenously as a 2 hour infusion at 400 mg/m² one week prior to the commencement of radiotherapy. It is then given and as a 1 hour infusion at 250 mg/m² once per week during weeks 1, 2, 3, 4 and 5 of radiotherapy. There is to be equal spacing between infusions.

Cetuximab must be administered under the supervision of a physician experienced in the use of antineoplastic medical products. Close monitoring is required during the infusion and for at least one hour after the end of the infusion. Availability of resuscitation equipment must be ensured.

Prior to cetuximab infusion, patients must receive premedication with an antihistamine (e.g. chlorpheniramine). Recently the MABEL study has demonstrated that the rate of severe (grade 3 and 4) infusion-related reactions in patients receiving cetuximab was 7.1% for 422 patients receiving premedication with an antihistamine alone versus 1.1% for 700 patients receiving any antihistamine plus a corticosteroid (Siena et al,'07). In the light of these data it is recommended that patients within the EXCITE trial should receive premedication using a corticosteroid, for example 8 mg of intravenous dexamethasone, in addition to an antihistamine.

Drug supply: Drug supply of cetuximab will be from special trial stock. The trial centre will inform Merck when all necessary approvals for a centre have been received. Centres should arrange initial supplies once their first patient is screened. Further supplies will be coordinated by hospital pharmacies directly with Merck using a drug request form. The monoclonal antibody is supplied at a concentration of 5mg/ml. The starting dose is 400mg/m² (=80ml/m²). 'Clinical trial' labelling will be provided by Merck in compliance with

regulatory requirements and additional accountability records need to be maintained by the pharmacy.

At the end of the trial the CTC will inform participating sites of the procedure for unused drug return/destruction.

Cetuximab side effects: In approximately 5% of patients hypersensitivity reactions may occur during treatment with cetuximab, approximately half of these reactions being severe.

Mild or moderate reactions (grade 1 or 2) include symptoms such as fever, chills, nausea, rash or dyspnoea. Severe hypersensitivity reactions (grade 3 or 4) usually occur during or within 1 hour of the initial cetuximab infusion, but may occur after several hours or with subsequent infusions, therefore it is recommended to warn patients of the possibility of late onset infusion-related reactions and instruct them to contact their physician. Symptoms include the rapid onset of airway obstruction (bronchospasm, stridor, hoarseness, difficulty in speaking), urticaria, and/or hypotension.

Recently the MABEL study has demonstrated that premedication with corticosteroids can reduce the rate of infusion related reactions for patients receiving cetuximab (see Section 8.2.3 above).

Conjunctivitis may be expected in approximately 5% of patients. Dyspnoea has been reported in 25% of patients with end stage colorectal cancer.

Skin reactions will develop in more than 80% of patients: approximately 15% of these are severe (\geq grade 3). They mainly present as acne-like rash affecting face, upper chest and back. On longer term therapy paronychia can develop in approximately 10% of patients and can be painful. The majority of skin reactions develop within the first 1-3 weeks of therapy. They generally resolve, without sequelae, following the cessation of treatment if the recommended adjustments in dose regimen are followed (see dose modifications Section 8.4.4-8.4.6).

Cetuximab precautions: Cetuximab is contraindicated in patients with known severe (grade 3 or 4) hypersensitivity reactions to cetuximab. There are no specific drug interactions documented with cetuximab. However, any agent that may interfere with the immune system of the patient should preferably be avoided except the indicated study regimen and necessary supportive treatment (including corticosteroids, antiemetics etc).

8.2.4 Irinotecan

Administration: Irinotecan is given as a 60 minute intravenous infusion in 250 mls of normal saline during weeks 1, 2, 3 and 4 of radiotherapy (with equal, weekly spacing between infusions).

Patients are recommended to receive premedication of atropine sulphate subcutaneously prior to irinotecan infusion to help prevent cholinergic syndrome.

Irinotecan must not be administered earlier than one hour after the end of the cetuximab infusion.

Patients should not receive St. Johns Wort whilst receiving irinotecan therapy.

Drug supply:

Patients 1-40:

Irinotecan for the first 40 patients will be from special trial stock, supplied by Pfizer and distributed by Aptuit. Supplies will be coordinated by CTC who will liaise with the hospital pharmacies directly.

'Clinical trial' labelling will be provided by Pfizer in compliance with regulatory requirements and additional accountability records will need to be maintained by the pharmacy.

At the end of the trial the CTC will inform participating sites of the procedure for unused drug return/destruction.

Patients 41-80:

Irinotecan for the remaining 40 patients will be from routine hospital supply and will require 'clinical trial' labelling by the site pharmacy in compliance with regulatory requirements. No additional accountability records other than the pharmacy's standard tracking/dispensing log are required. Unused irinotecan should be disposed of as per hospital policy.

Irinotecan side effects: When used as a single agent the major dose-limiting side effects of irinotecan are neutropenia and delayed diarrhoea.

Other toxic effects include a cholinergic-like syndrome (with 'early' diarrhoea, abdominal cramps, profuse perspiration, salivation and lacrimation), nausea, vomiting, constipation, mucositis, asthenia and alopecia.

Irinotecan precautions: Irinotecan and its metabolites are cleared by biliary excretion and patients with cholestasis have delayed clearance. If hepatobiliary function deteriorates below eligibility criteria limits during treatment, irinotecan should not be given.

8.2.5 Radiotherapy TARGET VOLUME DEFINITION

All patients will undergo contouring of their treatment volume using CT planning scans. Conventional fluoroscopy simulation is not permitted.

The radiotherapy treatment planning process will require: -

- A CT planning scan using CT slices of not more than 5mm thickness.
- All available diagnostic imaging (including pelvic MRI), together with clinical information such as that obtained from examination under anaesthetic.
- A digital rectal examination for the distal tumour extent by the planning clinical oncologist.

Patients should be preferably scanned (and treated) prone although supine is allowed in elderly patients or those with a defunctioning stoma in whom the prone position is not feasible. A radio-opaque anal marker should be used during planning CT to identify the anal margin. Patients should have a comfortably full bladder prior to the CT scan and during radiotherapy. Patients are scanned to include the superior aspect of L5, to 2cm inferior to the anal marker in order to ensure coverage of the whole of the pelvis, recto sigmoid and rectum. Small bowel contrast with Gastrografin (20mls in 1 litre of water approximately 1 hour prior to scan) is recommended to delineate small bowel in the pelvis and to determine if this can be safely excluded from the planning target volume.

The following target volumes will be defined. Some institutions will be able to co-register diagnostic MRI and CT planning scans although this is not mandatory.

Gross tumour volume (GTV): As much of the tumour is identified using diagnostic MRI scans to assist. On each slice all macroscopic visible tumour is outlined. Tumour involving large intramural veins or extra nodal deposits, imaged on MRI should also be included. The discontinuous nature of many rectal cancers with extra-nodal deposits may require the demarcation of more than one GTV area.

Clinical target volume (CTV): the volume of tissue that includes the GTV but also takes account of potential microscopic spread of the primary tumour including the mesorectal

subsite, the posterior pelvic subsite, regions at risk of lymph node spread and, for lower third rectal cancers, the inferior pelvic subsite (Roels et al,'06).

CTV for LOWER THIRD rectal tumours (0-5 cm from anal verge on rigid sigmoidoscopy) Posterior: Along the inner bony edge of the sacrum.

Anterior: GTV + 1cm, or mesorectal fascia + 1cm, whichever is most anterior. **Lateral**: Contoured around the bony lateral pelvic side wall.

Superior: GTV + 2cm or 1cm inferior to the S2/3 junction, whichever is the most superior. (The PTV would not normally extend superiorly to the sacral promontory). **Inferior**: GTV+2cm but the inferior pelvic subsite should also be included (Roels et al,'06). (The inferior pelvic subsite includes the ischiorectal fossa and the internal and external anal sphincter, with the penile bulb as the anterior border. Laterally the ischiorectal fossa is bounded by the fascia of internal obturator muscle and the ischial tuberosity. Posteriorly the border of the ischiorectal fossa is coccyx and the surface of gluteal muscle).

CTV for MIDDLE THIRD rectal tumours (5-10 cm from anal verge on rigid sigmoidoscopy) Posterior: Along the inner bony edge of the sacrum.

Anterior: GTV + 1cm, or mesorectal fascia + 1cm, whichever is most anterior.

Lateral: Contoured around the bony lateral pelvic side wall.

Superior: GTV + 2cm. (The PTV would not normally extend superiorly to the sacral promontory).

Inferior: GTV + 2 cm or 1 cm superior to the anorectal junction, whichever is the more inferior. (If the anorectal junction is used then a Foley catheter with the balloon inflated can be used to determine the level of the anorectal junction if necessary, in order to avoid including the anal sphincters in the CTV).

CTV for UPPER THIRD rectal tumours (10-12 cm from anal verge on rigid sigmoidoscopy) Posterior: Along the inner bony edge of the sacrum.

Anterior: GTV + 1cm, or mesorectal fascia + 1cm, whichever is most anterior.

Lateral: Contoured around the bony lateral pelvic side wall.

Superior: GTV + 2cm or 1 cm below the sacral promontory, whichever is the most superior.

Inferior: GTV + 2 cm.

Planning target volume (PTV): This adds a safety margin around the CTV to account for variation in patient and tumour position. A 1cm margin is applied in all directions to the CTV to derive the PTV.

Treatment delivery

The PTV is treated with any combination of at least 3 coplanar or non-coplanar 3D conformal fields, at the clinician's discretion. These are shaped to deliver the specified dose to the target while restricting the dose to the normal surrounding tissues using either MLC or custom-made blocks.

Radiation therapy should be delivered with effective photon energies of more than 6 MV generated by a linear accelerator. 3-D conformal radiotherapy is permitted. Mixed beams are allowed with higher photon energy for the lateral beams compared to the posterior beam.

A total dose of 45Gy in 25 daily fractions over a total time of 5 weeks should be delivered treating 5 days per week, 1 fraction per day, 1.8Gy per fraction. All fields must be treated during one treatment session. It is conventional to report the dose to the ICRU reference point, the maximum dose to the PTV and the minimum dose to the PTV. The isocentric treatment plan is usually specified to receive 100% with the 95% isodose line encompassing the PTV and no more than +5% and -5% in homogeneity within the target volume.

Normal critical tissues such as small bowel, femoral heads, ureter and bladder can be contoured and doses to these organs kept to a minimum. It appears that the small bowel is often close to the target volume, and the dose should be specified such that not more than 250 ml of small bowel receives in excess of 45Gy.

Verification and correction procedures

The rectum does move during a course of radiotherapy (Roeske et al 1995, Lebesque et al 1995). However, there is little data to quantify rectal motion and set up variation. Anatomical considerations suggest the rectum is more fixed at the distal end than proximally.

Verification of CT-contoured plans can be carried out prior to treatment commencing using either conventional simulator images or using DRRs as the reference images.

[figure not shown]

Figure 2: Radiotherapy planning diagram for lower rectal cancers

[figure not shown]

Figure 3: Radiotherapy planning diagram for upper third rectal cancers

Portal imaging

Portal imaging for verification of isocentre position and treatment fields should be acquired on the first treatment session both for AP and lateral images and compared to the reference images. Electronic portal imaging (EPI) can monitor set-up displacement on a daily basis in the initial phase of treatment (Tinger 1996). Simulator or DRR reference images can be compared with portal images manually or via automatic co-registration.

Fields should be moved if they fall outside an agreed tolerance level – usually 5 mm for patients who are treated prone. This process also allows clinicians and radiographers to evaluate the treatment field set-up with respect to bony landmarks and to assess and correct any systematic errors. The MLC configuration can also be verified for consistency and reproducibility. It is recommended to measure set up accuracy on a weekly basis.

